## Medical history

Medical history findings (i.e. previous diagnoses, diseases or surgeries) meeting all criteria listed below will be collected:

- Not pertaining to the study indication.
- Started before signing of the informed consent.
- Considered relevant to the study.

Detailed instructions on the differentiation between (i) medical history and (ii) adverse events can be found in Section 11 (Definitions).

## Efficacy

Efficacy variables to be measured include response rate (RR), progression-free survival (PFS), disease control rate (DCR) and overall survival (OS).

Response rate (RR) is defined as the percentage of subjects with a partial response (PR) or complete response (CR) as defined by RECIST criteria (see Appendix A). PFS will be measured from the date of randomization until disease progression or death from any cause. DCR will be the rate of CR, PR and stable disease (SD) combined together. OS will be measured from the date of randomization until death from any cause.

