## Synopsis

Title	Regorafenib in Adults $\geq$ 65 Years with Metastatic Colorectal Cancer: A Phase II Study
Clinical study phase	Phase II
Primary study objective	To assess grade 3-5 toxicity rates of regorafenib in older adults with implementation of focused education and support initiatives
Indication	Refractory metastatic colorectal cancer (mCRC)
Diagnosis and main criteria for inclusion	
 
1. Histologically or cytologically confirmed colorectal carcinoma
 
2. Evidence of measurable (by RECIST criteria) metastatic disease
 
3. Age 65 years or over
 
4. Progression of disease on previous therapy, deemed not a candidate for further standard therapy by treating oncologist, or patient declines other options
 
5. ECOG PS 0-1
 

Study design	Single-arm, open label Phase II study
Type of control	Historical
Number of subjects	60
Plan for statistical analysis	
Adverse events will be grouped by system organ class and graded using NCI CTCAE version 4.0. Descriptive statistics for grade 3/4 toxicity rates and all-grade skin (HFS) toxicity will be assessed. Relative dose intensity for regorafenib will be calculated.
 
Based on expected grade 3-4 toxicity rates of 40-50%, a sample size of 60 patients will give approximately 10% margin of error with 95% confidence interval.
 
Secondary outcomes for efficacy will be response rate (RR), progression-free survival (PFS) and overall survival (OS). Kaplan-Meier curves will be used to estimate median PFS and OS.

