### Exclusion Criteria

- Previous treatment with regorafenib.
- Systemic therapy for metastatic CRC within 28 days of initiating study treatment.
- Previous assignment to treatment during this study. Subjects permanently withdrawn from study participation will not be allowed to re-enter study.
- Uncontrolled hypertension (systolic pressure  $>140$  mm Hg or diastolic pressure  $> 90$  mm Hg [NCI-CTCAE v4.0] on repeated measurement) despite optimal medical management.
- Active or clinically significant cardiac disease including:
  - Congestive heart failure – New York Heart Association (NYHA)  $>$  Class II.

- Active coronary artery disease.
- Cardiac arrhythmias requiring anti-arrhythmic therapy other than beta blockers, calcium channel blockers or digoxin.
- Unstable angina (anginal symptoms at rest), new-onset angina within 3 months before randomization, or myocardial infarction within 6 months before randomization.
- Evidence or history of bleeding diathesis or coagulopathy.
- Any hemorrhage or bleeding event  $\geq$  NCI CTCAE Grade 3 within 4 weeks prior to start of study medication.
- Subjects with thrombotic, embolic, venous, or arterial events, such as cerebrovascular accident (including transient ischemic attacks) deep vein thrombosis or pulmonary embolism within 6 months of informed consent.
- History of other active malignancy within past 2 years (excluding non-melanoma skin cancer).
- Patients with pheochromocytoma.
- Known history of human immunodeficiency virus (HIV) infection or current chronic or active hepatitis B or C infection requiring treatment with antiviral therapy.
- Ongoing infection  $>$  Grade 2 NCI-CTCAE v4.0.
- Symptomatic metastatic brain or meningeal tumors.
- Presence of a non-healing wound, non-healing ulcer, or bone fracture.
- Major surgical procedure or significant traumatic injury within 28 days before start of study medication.
- Renal failure requiring hemo- or peritoneal dialysis.
- Dehydration Grade  $\geq 1$  NCI-CTCAE v4.0.
- Patients with seizure disorder requiring medication.
- Persistent proteinuria  $\geq$  Grade 3 NCI-CTCAE v4.0 ( $> 3.5$  g/24 hrs, measured by urine protein: creatinine ratio on a random urine sample).
- Interstitial lung disease with ongoing signs and symptoms at the time of informed consent.
- Pleural effusion or ascites that causes respiratory compromise ( $\geq$  NCI-CTCAE version 4.0 Grade 2 dyspnea).
- History of organ allograft (including corneal transplant).

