### Study Treatment

The initial screening period is 14 days from the date of consent. Once approved, by the coordinating site, an additional 14 day period is granted for scheduling, in which subjects must start treatment.

Regorafenib will be administered as monotherapy during the study. 120 mg qd (starting dose) will be administered for 3 weeks on /1 week off. One cycle is 28 days. Study treatment must be initiated within 14 days of registration.

Three 40-mg regorafenib tablets (starting dose) should be taken once a day with approximately 8 fluid ounces (240 mL) of water after a low-fat (<30% fat) meal. Some examples of low fat meals are:

- Two slices of white toast with 1 tablespoon of low-fat margarine and 1 tablespoon of jelly and 8 ounces (240 mL) of skim milk (approximately 319 calories and 8.2 g of fat).
- One cup of cereal (i.e. Special K), 8 ounces (240 mL) of skim milk, one piece of toast with jam (no butter or marmalade), apple juice, and one cup of coffee or tea (2 g fat, 17 g protein, 93 g of carbohydrate, 520 calories).

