## Follow-up Period

### Follow-up Prior to Progression

- Patients who come off treatment for reasons other than progression of disease will have physical exams performed at least every 3 months or earlier as clinically indicated until the follow-up period is terminated (see Reasons for Follow-up Termination). Frequency of radiographic studies will be at the discretion of the treating physicians.
- After disease progression, follow-up assessments will occur every 6 months and will include subsequent anti-neoplastic therapy and survival status of the patient until the follow-up period is terminated (see Reasons for Follow-up Termination). Physical exams, and all other assessments, are at the discretion of the treating physicians.

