### Termination of Follow-up

Patients whose follow-up period terminates should have the final date of contact recorded in the End of Study CRF in REDCap.

- For patients in follow-up at completion of the study, please use the study termination date
- Patients found to be deceased in the follow-up period should have their date of death recorded in the End of Study CRF.
- For patients who withdraw consent from follow-up, use the date the patient withdrew consent. Notify the Coordinating Center's data manager of the patient withdrawal of consent from follow-up, along with supporting documentation, should this occur.
- For patients who meet the criteria to be lost-to follow-up, enter the last date of known contact with the patient, along with comments in the CRF indicating the patient is lost-to follow-up.

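### PFS and OS start at a randomization date that a single-arm trial does not have; with no OS censoring rule or survival check at closure, OS can also be overstated

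*Combined protocol and SAP*

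**What the plan says.** The Synopsis describes a "Single-arm, open label Phase II study" with a historical control. The Efficacy part of section 10 nevertheless defines both time-to-event endpoints from randomization: "PFS will be measured from the date of randomization until disease progression or death from any cause", and "OS will be measured from the date of randomization until death from any cause". The Exclusion Criteria in section 5 use the same event for the cardiac windows: "new-onset angina within 3 months before randomization, or myocardial infarction within 6 months before randomization".

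The dates that do exist are consent, registration and first dose. Study Treatment in section 7 allows 14 days of screening from consent and a further 14 days for scheduling, and says "Study treatment must be initiated within 14 days of registration".

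Statistical and analytical plans in section 12 gives Kaplan-Meier estimates of the median for PFS and OS. It names no time origin, censoring rule or data cut-off.

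The only instruction on closing dates is under Termination of Follow-up: "Patients whose follow-up period terminates should have the final date of contact recorded in the End of Study CRF in REDCap". One of its bullets reads "For patients in follow-up at completion of the study, please use the study termination date". Survival information after progression is sparse: "After disease progression, follow-up assessments will occur every 6 months", and the Table of Assessments repeats that interval.

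**The concern.** There are two faults, one at each end of the survival time.

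**Start.** With no randomization, an analyst has to choose a date after the fact. Three candidates exist, and the plan does not choose among them. The angina and infarction windows for eligibility hang on the same missing date.

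**End.** A patient who has progressed may have been last seen alive up to 6 months before the study closes. The form records that patient's final contact as the termination date whether or not anyone made contact then. If that field becomes the OS censoring date, a patient who died unseen in the interval counts as alive to study end. The error goes one way: OS looks longer.

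No test is planned on PFS or OS. But efficacy is the first secondary objective and the control is historical, so readers are likely to set the medians beside those quoted for CORRECT in section 1 (1.9 months for PFS, 6.4 months for OS). An arbitrary start and a possible upward bias in OS both weaken that reading.

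**Working it through.** The plan states no design figure for PFS or OS, so there is none to reproduce.

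**Step 1: shift from the choice of start date.** Inputs: 14 days from registration to first dose, and 14 + 14 = 28 days from consent to first dose (section 7); reference medians 1.9 and 6.4 months (section 1).

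- Maximum for one patient: 14 / 30.44 = 0.46 months; 28 / 30.44 = 0.92 months.
- Average, assuming delays spread evenly over the window and added to exponential times with those medians (400,000 draws): median PFS moves by 0.23 months (registration) or 0.47 (consent), and median OS by 0.23 or 0.46.
- Relative to a PFS median of 1.9: 0.23 / 1.9 = 12%; 0.47 / 1.9 = 25%.
- If median PFS falls instead at the first 12-week scan, 84 / 30.44 = 2.76 months: 0.23 / 2.76 = 8%; 0.47 / 2.76 = 17%.
- Relative to an OS median of 6.4: 0.23 / 6.4 = 4%; 0.46 / 6.4 = 7%.

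**Step 2: how many patients die between contacts.** With exponential OS and a median of 6.4 months, the chance that a patient alive at one contact dies before the next is 1 − 0.5^(6/6.4) = 48%.

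**Step 3: effect on the Kaplan-Meier estimate.** The time from last entry to closure is not stated, so it is varied. The simulation used 60 patients, entry at 3.5 per month (the midpoint of the planned 3 to 4), exponential OS (median 6.4) and PFS (median 1.9), contact every 6 months after progression, and 1,500 replicates per setting. Deaths are fully known until progression, or until 1 month after it; these two cases give the ranges. The table compares full status at closure with censoring at the termination date when no later death between contacts is known.

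| Closure after last entry | Median OS, full status | Median OS, termination date | Rise in median | 12-month OS, termination date (full status 27–28%) | Deaths missed of 60 |
|---|---|---|---|---|---|
| 3 months | 6.5 | 7.4–7.7 | 0.8–1.2 | 35–36% | 5–6 |
| 6 months | 6.3–6.4 | 6.7–7.0 | 0.4–0.6 | 32–33% | 5 |
| 9 months | 6.3–6.4 | 6.4–6.5 | 0.1 | 30–31% | 4 |
| 12 months | no change | no change | 0 | 28–29% | 3 |

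The rise in 12-month OS is thus 7–9, 5–6, 3 and 1 points. If half of the deaths between contacts are known, the median rises by 0.4–0.5 months (closing at 3 months) and 0.2–0.3 (at 6).

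**Step 4: sensitivity.** A second simulation used entry at 3 and 4 per month, uniform accrual and monthly contact before progression.

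- Closing at 3 months, the median moved from 6.43 to 7.50 and from 6.40 to 7.97, a rise of 1.07 and 1.57.
- Closing at 6 months, from 6.28 to 6.66 and from 6.34 to 6.92, a rise of 0.38 and 0.58.
- Closing at 12 months, no change.

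**Step 5: is censoring at the date last known alive enough?** If neither deaths nor survivors come to light between contacts, it stays close to the truth (median 6.2–6.5 months, 12-month OS 27–28%). If half the deaths are heard of but survivors are not re-dated, it errs downward: 12-month OS is 24–25% against 27%, closing at 3 or 6 months. Checking every patient at one cut-off date avoids both errors.

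**The case against.** The strongest reply accepts the randomization error but disputes its weight.

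- **Consent is an unlikely origin.** Patients who leave before assignment or first dose are screen failures, so the realistic choice is registration or first dose, and the average shift is 0.23 months. The 12-weekly scans are a coarser limit on PFS than that. This is fair, but the text excludes none of the three dates.
- **The form is not a censoring rule.** The OS bias needs an analyst to use that field and deaths to be unknown at closure; visit-level survival records also exist. This is true, and the finding is conditional for that reason. It is still the only closing date the protocol tells sites to record.
- **Other provisions may reveal deaths.** Lost-to Follow-up asks sites to pursue survival status until follow-up ends. Termination of Follow-up records the date of death for patients found to have died. Section 11 asks for deaths during the trial to be reported within 24 hours. These would reduce the bias, but none requires a dated status check at closure.
- **Chance is larger.** Even with complete status, a Kaplan-Meier median from 60 patients ranges over roughly 4.3 to 9 months. That stands, but it does not excuse an avoidable error in one direction.
- **PFS also lacks a censoring rule.** This is correct, and it adds to the gap.

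**Conclusion.** The concern holds. The start date is an outright contradiction: PFS and OS cannot be computed as defined. The choice left open is worth on average 0.23 to 0.47 months of median PFS, assuming evenly spread delays, and about 4% to 7% of a 6.4-month median OS.

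The closing-date problem is conditional. It arises only if the End of Study date is used to censor OS, and only for patients still in follow-up at closure, since patients lost to follow-up carry their last known contact. Its size depends on a closing time that the documents do not give. It is material for the median when closure comes soon after last entry (up to about 1.6 months across the settings tried at 3 months), and has gone by 12 months. The results rest on exponential times, steady accrual and CORRECT's medians. Sites that hear of deaths early would show less bias.

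This should be fixed, but it does not threaten the trial's main conclusion.

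**What to change.** 1. In the Efficacy part of section 10, replace randomization with one existing date as time zero for both PFS and OS, and repeat it in section 12. First dose of regorafenib would match the safety population, which is every patient given at least one dose.
2. Reconcile the cardiac windows in the Exclusion Criteria with a date that exists.
3. Add an OS censoring rule to section 12. Every patient's survival status is checked at a common cut-off date, and those confirmed alive are censored at that date. Only where status cannot be obtained is the patient censored at the date last known alive.
4. Amend the End of Study form instruction so that the termination date is entered only for patients confirmed alive on it.
5. State the PFS censoring rule in the same amendment.

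The cost is a few sentences, one form instruction and at most 60 calls or record checks at closure. Sample size and the primary endpoint do not change.

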## 11. Safety

All subjects who receive at least one dose of study treatment will be valid for the safety analysis.

All observations pertinent to the safety of the study treatment will be recorded and included in the final report.

Safety variables include the following: AEs, laboratory changes (complete blood counts, electrolytes, chemistry, and coagulation) and changes in vital signs (blood pressure, heart rate, respiratory rate, and temperature).

All AEs whether considered drug-related or not, will be reported in with a diagnosis, start/stop dates, action taken, whether treatment was discontinued, any corrective measures taken, outcome, and other possible causes. For all events, the relationship to treatment and the intensity of the event will be determined by the investigator.

This trial will use the NCI-CTCAE v4.0 criteria for assessment of toxicity and SAE reporting with regard to toxicity grade.

## Adverse events

Investigators should refer to the Safety Information section of the current IB for regorafenib, including the DCSI (development core safety information), for the expected side effects of regorafenib. As with any agent, there is always the potential for unexpected AEs, including hypersensitivity reactions. The IB will be updated if any new relevant safety data are obtained.

Therapeutic monitoring should be performed following dose selection or modification of regorafenib, in a manner consistent with the local clinical standard of care. In general, subjects should be closely monitored for side effects of all concomitant medications regardless of the path of drug elimination.

All concomitant medications must be recorded in the subject's source documentation.

Subjects must be carefully monitored for AEs. This monitoring also includes clinical laboratory tests. Adverse events should be assessed in terms of their seriousness, intensity, and relationship to the study drug, or other chemotherapy/treatment.

## Definitions

### Definition of adverse event (AE)

In a clinical study, an AE is any untoward medical occurrence (i.e. any unfavorable and unintended sign [including abnormal laboratory findings], symptom or disease) in a patient or clinical investigation subject after providing written informed consent for participation in the study. Therefore, an AE may or may not be temporally or causally associated with the use of a medicinal (investigational) product.

A surgical procedure that was planned prior to the start of the study by any physician treating the subject should not be recorded as AE (however, the condition for which the surgery is required may be an AE if worsens compared to baseline).

- Conditions that started before signing of informed consent and for which no symptoms or treatment are present until signing of informed consent are recorded as medical history (e.g. seasonal allergy without acute complaints).
- Conditions that started before signing of informed consent and for which symptoms or treatment are present after signing of informed consent, at *unchanged intensity*, are recorded as medical history (e.g. allergic pollinosis).
- Conditions that started or deteriorated after signing of informed consent will be documented as adverse events.

### Definition of serious adverse event (SAE)

An SAE is classified as any untoward medical occurrence that, at any dose, meets any of the following criteria (a – f):

- a. Results in death.
- b. Is life-threatening.

The term 'life-threatening' in the definition refers to an event in which the patient was at risk of death at the time of the event, it does not refer to an event which hypothetically might have caused death if it were more severe.

- c. Requires inpatient hospitalization or prolongation of existing hospitalization.

A hospitalization or prolongation of hospitalization will not be regarded as an SAE if at least one of the following exceptions is met:

- The admission results in a hospital stay of less than 12 hours.
- The admission is pre-planned.  
(i.e. elective or scheduled surgery arranged prior to the start of the study)
- The admission is not associated with an AE.  
(e.g. social hospitalization for purposes of respite care).

However, it should be noted that invasive treatment during any hospitalization may fulfill the criterion of ‘medically important’ and as such may be reportable as an SAE dependent on clinical judgment. In addition, where local regulatory authorities specifically require a more stringent definition, the local regulation takes precedence.

- d. Results in persistent or significant disability / incapacity.

Disability means a substantial disruption of a person’s ability to conduct normal life’s functions.

- e. Is a congenital anomaly / birth defect.

- f. Is another medically important serious event as judged by the investigator.

### **Classifications for adverse event assessment**

All AEs will be assessed and documented by the investigator according to the categories detailed below.

#### **Seriousness**

For each AE, the seriousness must be determined according to the criteria given in Section 11 (Definitions).

#### **Intensity**

The intensity of the AE is classified according to the CTCAEv4.0. Grade refers to the severity (intensity) of the AE:

**CTCAEv4 Grade 1:** mild; asymptomatic or mild symptoms; clinical or diagnostic observations only; intervention is not indicated.

**CTCAEv4 Grade 2:** moderate; minimal, local, or noninvasive intervention is indicated; limiting to age-appropriate instrumental activities of daily living (ADL; instrumental ADL refers to preparing meals, shopping for groceries or clothes, using the telephone, managing money, etc).

**CTCAEv4 Grade 3:** Severe or medically significant but not immediately life threatening; hospitalization or prolongation of hospitalization is indicated; disabling; limiting to self care ADL (self care ADL refers to bathing, dressing and undressing, feeding self, using the toilet, taking medications, and not bedridden).

**CTCAEv4 Grade 4:** life-threatening consequences; urgent intervention is indicated.

**CTCAEv4 Grade 5:** death due to an AE.

### **Causal relationship**

The assessment of the causal relationship between an AE and the administration of treatment is a clinical decision based on all available information.

The assessment is based on the question whether there was a “reasonable causal relationship” to the study treatment in question.

Possible answers are “yes” or “no”.

An assessment of “no” would include:

1. The existence of a clear alternative explanation, e.g. mechanical bleeding at surgical site.  
or
2. Non-plausibility, e.g. the subject is struck by an automobile when there is no indication that the drug caused disorientation that may have caused the event; cancer developing a few days after the first drug administration.

An assessment of “yes” indicates that there is a reasonable suspicion that the AE is associated with the use of the study treatment.

Factors to be considered in assessing the relationship of the AE to study treatment include:

- The temporal sequence from drug administration: The event should occur after the drug is given. The length of time from drug exposure to event should be evaluated in the clinical context of the event.
- Recovery on drug discontinuation (de-challenge), recurrence on drug re-introduction (re-challenge):
- Subject’s response after de-challenge or subjects response after re-challenge should be considered in the view of the usual clinical course of the event in question.
- Underlying, concomitant, intercurrent diseases:  
Each event should be evaluated in the context of the natural history and course of the disease being treated and any other disease the subject may have.
- Concomitant medication or treatment:  
The other drugs the subject is taking or the treatment the subject receives should be examined to determine whether any of them may be suspected to cause the event in question.
- The pharmacology and pharmacokinetics of the study treatment:  
The pharmacokinetic properties (absorption, distribution, metabolism and excretion) of the study treatment, coupled with the individual subject’s pharmacodynamics should be considered.

